## Adverse Reaction

Any AE caused by a drug is considered an adverse reaction.

### 10.2 Causality of AEs

Causality assessment has become a common routine procedure in pharmacovigilance. Causality assessments can decrease disagreement between assessors, classify relationship likelihood and improvement of scientific evaluation.

Limitations of causality assessment are following:

It can NOT assess accurate quantitative measurement of relationship likelihood

It can NOT distinguish valid from invalid cases

It can NOT prove the connection between drug and event

It can NOT quantify the contribution of a drug to the development of an adverse event

All adverse events (AEs) must have their relationship to study intervention assessed by the clinician who examines and evaluates the participant based on temporal relationship and his/her clinical judgment. The degree of certainty about causality will be graded using the 2 categories below. In a clinical trial, the study product must always be suspect.

**Related:** The AE is known to occur with the study intervention, there is a reasonable possibility that the study intervention caused the AE, or there is a temporal relationship between the study intervention and event. Reasonable possibility means that there is evidence to suggest a causal relationship between the study intervention and the AE.

**Not Related:** There is not a reasonable possibility that the administration of the study intervention caused the event, there is no temporal relationship between the study intervention and event onset, or an alternate etiology has been established.

### 10.3 Categorization of AEs

AEs will be graded according to the FDA Guidance for Industry *Toxicity Grading Scale for Healthy Adult and Adolescent Volunteers Enrolled in Preventive Vaccine Clinical Trials* and reported in the detail indicated on the CRF. The definitions are as follows:

Grade 1 Mild: discomfort noticed, but no disruption to daily activity

Grade 2 Moderate: discomfort sufficient to reduce or affect normal daily activity

Grade 3 Severe: Inability to work or perform normal daily activity

## Grade 4 Potentially Life-threatening

### **10.4 Reporting of SAEs and Suspected Unexpected Serious Adverse Reactions (SUSARs)**

Any SAE, including death resulting from any cause, which occurs to any subject participating in this study must be reported by investigator to the sponsor **within 24 hours** (and IRB as required) of first becoming aware of the SAE. The study sponsor will be responsible for notifying the FDA of any unexpected fatal or life-threatening suspected adverse reaction as soon as possible, but in no case later than 7 calendar days after the sponsor's initial receipt of the information. In addition, the sponsor must notify FDA and all participating investigators in an IND safety report of potential serious risks, from clinical trials or any other source, as soon as possible, but in no case later than 15 calendar days after the sponsor determines that the information qualifies for reporting

SAEs will be collected by the investigator from day 1 through 30 days after the administration of study medication. SAEs that occur within 30 days following cessation of the study treatment, must also be reported within the same timeframe. Any SAE that is judged by the investigator to be related to the study medication must be reported regardless of the amount of time since the last dose received. Follow-up information collected for any initial report of an SAE must also be reported to the sponsor (or its designee) within 24 hours of receipt by the investigator. All SAEs will be followed until resolution, stabilization of condition, or until follow-up is no longer possible. To fully understand the nature of any SAE, obtaining follow-up information is important. Whenever possible, relevant medical records such as discharge summaries, medical consultations, reports of radiographic studies, and clinical laboratory reports should be obtained.

In the event of death, regardless of cause, all attempts should be made to obtain the death certificate and any autopsy report, if performed. These records should be reviewed in detail, and the investigator should comment on any event, lab abnormality, or any other finding, noting whether it should be considered a serious or non-serious AE, or whether it should be considered as part of the subject's history. In addition, all events or other findings determined to be SAEs should be identified on the follow-up SAE form and the investigator should consider whether the event is related or not related to study drug.

### **10.5 IRB Reporting**

The investigators will report to the IRB the following according to the requirements of reviewing IRB:

- All SAEs, except deaths due to progressive disease
- Non-compliance to GCP or protocol deviations as required by IRB

IND Safety Reports and any unexpected incidences or problems during the trial may be also reportable to the IRB as per IRB requirement.

## **10.6 Quality Assurance and Quality Control**

Quality control (QC) procedures will be implemented to assure that any missing data will be communicated with sites for clarification and resolution.

Standard Operating Procedures (SOPs) should be available to monitors. Monitors will verify that all the clinical trial procedures are conducted, documented and reported in compliance with the protocol, ICH, GCP, GLP, GMP and other applicable regulatory requirements.

The investigational site will provide direct access to all trial related sites, source data/documents, and reports for the purpose of monitoring and auditing by the sponsor, and inspection by local and regulatory authorities.

## **10.7 Study Monitoring Plan**

Clinical site monitoring is conducted to ensure that the rights and well-being of trial participants are protected, that the reported trial data are accurate, complete, and verifiable, and that the conduct of the trial is in compliance with the currently approved protocol/amendment(s), with ICH GCP, and with applicable regulatory requirement(s).

Monitoring for this study will be performed by the Sponsor.

Details of clinical site monitoring will be documented in a separate Study Monitoring Plan (SMP). The SMP describes in detail who will conduct the monitoring, at what frequency monitoring will be done, at what level of detail monitoring will be performed, and the distribution of monitoring reports. In general monitoring visits would include pre-study visits (to qualify the site and investigators), study initiation visit, interim visits at appropriate frequency based on recruitment speed and need to clean data for dose-escalation decisions, and study closeout visits after database lock.

Independent audits may be conducted by the sponsor to ensure monitoring practices are performed consistently across all participating sites and that monitors are following the SMP.

Monitors are qualified by training and experience to monitor the progress of clinical trials. Personnel monitoring this study will not be affiliated in any way with the trial conduct.

A monitor(s)/sponsor representative(s) will meet with the investigator and his/her staff prior to the entrance of the first subject to review study procedures and methods of recording study data. After enrollment of the first subject, a monitor(s)/sponsor representative(s) will be assigned to periodically monitor each investigator site for study progress and to verify that standards of Good Clinical Practice (GCP) and/or ICH guidelines were followed.

The investigator is expected to prepare for the monitor visit, ensuring that all source documents, completed CRFs, signed consent forms and other study related documents are readily available for review.

FDA regulations require the Investigators to facilitate monitoring process. Monitors will evaluate adherence to the protocol, regulations, SOPs, human subject protection, study data, specifically data that could affect the interpretation of primary study endpoints. This is done through independent verification of study data with source documentation focusing on:

- Informed consent process
- Eligibility confirmation
- Drug administration and accountability
- Adverse events monitoring

### **10.8 Study Closure**

The investigator may terminate the study at any time in the interest of subject welfare. The sponsor may terminate the study prematurely at any time. Reasons for the closure of an investigational site or termination of a study may include:

- The Investigator fails to comply with the protocol or ICH/GCP guidelines
- Safety concerns
- Inadequate recruitment of subjects by the investigator
- Completion of the study

If the clinical study is prematurely terminated or suspended, the sponsor or CRO representative will inform the investigator and the regulatory authorities of the termination/ suspension and the reasons for the termination/suspension as appropriate. The investigator should promptly notify the IEC/IRB of the termination or suspension and provide reasons. The sponsor reserves the right to close the investigational site or terminate the study in its entirety at any time, for reasonable cause.

Premature termination of the study by either PI or sponsor will be governed under the terms of the contract between both parties.

### **10.9 Safety Review Committee (SRC)**

To ensure the safety of study subjects and integrity of the study data, a Safety Review Committee (SRC) consisting of the study Investigators, Study Director, designated Medical Monitor and/or other key study personnel will convene to review cumulative data for the study. SRC will conduct dose decision teleconference meeting before each dose escalation.

Before each dose escalation, the Investigators, Study Director and Medical Monitor(s), together, will review the safety data from the current cohort after enough subjects (7-8) have completed the first week. It will be determined whether escalation to the next dose level can proceed or whether dose level should be de-escalated.

## **11 STATISTICAL CONSIDERATIONS**

### **11.1 General Statistical Considerations**

Descriptive statistics will be utilized for all safety, efficacy, and PK parameters. Data will be summarized using descriptive statistics (number of subjects, mean, and median, standard deviation, minimum and maximum) for continuous variables and using frequencies and percentages for discrete variables.

In addition to descriptive summary, statistical testing will be performed to provide inferential summaries of group/subgroup comparison of endpoints. Univariate analyses will be conducted to determine the effects of key patient and disease characteristics on study endpoints, e.g., Two-sample *t*-test or Wilcoxon rank sum test will be used for continuous variables as appropriate and Chi-square test or Fisher's exact test for categorical variables. Kaplan-Meier method or log-rank test will be provided for time-to-event endpoints. For comparison of more than 2 groups, ANOVA test or Kruskal-Wallis test will be carried out. Multivariate analyses may be conducted to examining relationship between multiple variables and endpoints.

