### 4.2 Study Process

The trial will include a screening period, treatment period, and follow-up period of 30 days after administration. The screening period will be up to 28 days prior to investigational product administration. The screening process will initiate upon completion of the informed consent process. Once consent is provided by each participant, a thorough screening process will take place, including detailed medical history, physical examination, vital signs, concomitant medications, safety labs (see Table 1), 12 lead electrocardiogram, urine pregnancy test, urinalysis, serology panel (refer Table 1), assessment of inclusion and exclusion criteria. Upon completion of the screening, qualified subjects will be randomized to OsrHSA or placebo (6:2). Each enrolled subject will receive one single assigned dose of OsrHSA or placebo. The investigator and subjects will be blinded to treatment assignment. During the study, subjects will be evaluated for safety and toxicity, PK/PD, and activity of OsrHSA.

OsrHSA or placebo will be administered as single IV infusion at a rate lower than 2 ml/ min to the subjects. The actual start and stop times of the infusions, along with any interruptions in the infusion will be recorded. Subjects will have end-of-study (EOS) follow-up visits on Day 30 after infusion.

The planned doses are 20, 40, 80, 140, and 200 mg/kg (Table 2), dose level(s) higher than 200 mg/kg might be an option(s) based on emerging data from this study and ongoing China clinical trial, if that is the case, an amendment will be submitted.

The protocol for the repeat dose study will be submitted as an amendment to the IND after the single dose study has been completed and analyzed. The dose schedule of the repeat dose study will be based on results obtained from the single dose study. The safety of the dose that will be used in the repeat dose study will be established before the initiation of the repeat dose study.

Dose escalation will occur sequentially after review of safety data for each dosing cohort by the safety review committee (SRC). Dose escalation to the next dose level will proceed uninterrupted as long as no pre-defined DLT or stopping criteria are met.

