    - b. simultaneous use of hormonal contraceptives, starting at least 4 weeks prior to study drug administration and must agree to use the same hormonal contraceptive throughout the study, and condom for the male partner;
    - c. simultaneous use of diaphragm with intravaginally applied spermicide and male condom for the male partner, starting at least 21 days prior to study drug administration.
  - Male subjects who are not vasectomized for at least 6 months and who are sexually active with a non-sterile female partner must agree to use double methods of contraception below

from the first dose of randomized study drug until 90 days after their dose and must not donate sperm during their study participation period:

- a) simultaneous use of a male condom and, for the female partner, hormonal contraceptives (used since at least 4 weeks) or intra-uterine contraceptive device (placed since at least 4 weeks);
  - b) simultaneous use of a male condom and, for the female partner, a diaphragm with intravaginally applied spermicide.
7. Body mass index (BMI) 18-30 kg/m^2 and body weight  $\geq$  50.0 kg for males and  $\geq$  45.0 kg for females.
  8. Blood pressure  $\leq$  139/89 mm Hg.
  9. Subjects are able to follow the study protocol and complete the trial.
  10. At least 25% of the enrolled subjects will be of Asian descent, defined as Chinese, Japanese, Korean, Vietnamese, Hmong, and their offspring.

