### **11.2 Determination of Sample Size**

An estimated total of 40 subjects will enroll in this study. The sample size for this study was determined based on clinical, rather than statistical considerations. A projected sample size of 8 subjects per dosing cohort is considered to be of reasonable size to achieve the objectives of this single dose escalation trial. Other factors may contribute to the final sample size, which is dependent upon the observed safety and tolerability profile, and determines the number of subjects per dose cohort, number of replacements, as well as the number of dose escalations required to achieve the maximal proposed dose of the study drug.

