## 11.4 Statistical Analysis

### 11.4.1 PK Analysis

PK parameters will include  $T_{max}$ ,  $C_{max}$ ,  $AUC_{last}$ ,  $AUC_{\infty}$ ,  $t_{1/2}$ , CL, and  $V_z$ . The concentration-time data will be summarized by descriptive statistics (n, mean, and standard deviation, coefficient of variation, median, minimum, maximum, and geometric mean) according to dosing cohort and time of the study. PK parameters will be estimated using a non-compartmental method with WinNonlin (Pharsight Corp, Cary, North Carolina). Individual serum concentration of versus actual day will be tabulated and plotted by dose level (linear and log scales). Plots of the mean or median concentrations of OsrHSA will be presented by nominal day (linear and log scale) by dose level. If 3 cohorts complete in the study, linearity in PK parameters will be tested by fitting the model:  $\log(C_{max} \text{ or } AUC) = a + b * \log(\text{dose}) + \text{Dose}$ . Dose-proportionality will be tested using Power Model.

A population PK-based modeling approach may also be applied for PK characterization and PK covariate analyses. The steady state PK profile may be projected based on the population PK model. Population PK and PD data may be analyzed using modeling approaches and may also be pooled with data from other studies to investigate any association between investigational drug exposure and biomarkers or significant safety endpoints. Alternative dosing approach, e.g., body size-based or fixed dosing, may be evaluated using a population PK/PD approach. The results of these analyses, if performed, will be reported separately.

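### The committed tests of subject characteristics in Section 11.1 carry no dose term, so for dose-dependent endpoints they lose most of their power and are exposed to confounding with dose

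*Combined protocol and SAP*

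**What the plan says.** Section 11.1 makes a firm commitment: "Univariate analyses will be conducted to determine the effects of key patient and disease characteristics on study endpoints". For continuous endpoints it names the two-sample t-test or the rank-sum test ("Wilcoxon rank sum test will be used for continuous variables as appropriate"), and for categorical endpoints the chi-square or Fisher test. It does not name the characteristics, the endpoints or the subjects included, and it mentions no dose term and no stratification by cohort.

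Analyses that could include dose are optional. Section 11.1 adds that "Multivariate analyses may be conducted to examining relationship between multiple variables and endpoints", and Section 11.4.1 that "A population PK-based modeling approach may also be applied for PK characterization and PK covariate analyses". Neither names dose as a covariate. Dose is modelled only for linearity and dose proportionality in Section 11.4.1.

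On the design, Section 4.2 states: "The planned doses are 20, 40, 80, 140, and 200 mg/kg". Table 2 gives 8 subjects per cohort, 6 on OsrHSA and 2 on placebo. Section 11.2 gives the total ("An estimated total of 40 subjects will enroll in this study") and its basis ("The sample size for this study was determined based on clinical, rather than statistical considerations"). The only characteristic with a stated share is in Section 5.2: "At least 25% of the enrolled subjects will be of Asian descent". That minimum is overall, not per cohort, and Section 5.8 describes no stratified randomization. Section 11.4.2 rules out statistical tests of safety endpoints.

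**The concern.** Dose is the one large source of variation that this design creates on purpose. A two-sample test of, say, sex or Asian descent on Cmax that leaves dose out has two weaknesses.

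- **Precision.** The spread between 20 and 200 mg/kg goes into the error term, and a moderate difference in exposure between groups is hard to see.
- **Bias.** Cohorts are filled one after another. If a group is recruited mainly into early or late cohorts, the difference in dose appears as an effect of the characteristic.

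The sponsor has set a minimum share for one ethnic group, so a comparison by ethnicity is likely to be looked at. As the plan is worded, the committed version of that comparison is the weak one, and the version that could handle dose may never be run.

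**Working it through.** **The plan's own figure.** 5 cohorts × 8 = 40 subjects, of whom 5 × 6 = 30 receive OsrHSA and 10 placebo. This matches Section 11.2. No power, alpha, SD or effect size is stated, so there is no power claim to reproduce.

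**Assumptions not in the documents.** Two-sided alpha 0.05; exposure proportional to dose; within-dose SD s of ln(exposure) from 0.2 to 0.4; a true ratio of 1.3 between groups; OsrHSA recipients only. Two splits are used: 15 v 15 (for example, sex) and 8 v 22 (25% of 30 is 7.5, rounded to 8).

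**Spread due to dose.** The ln doses are 2.996, 3.689, 4.382, 4.942 and 5.298. Their mean is 4.261 and their SD 0.835 (0.849 as a sample SD over the 30 subjects).

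**Error SD.** Pooled: S = √(s² + 0.835²), which is 0.859, 0.887 and 0.926 for s = 0.2, 0.3 and 0.4. With dose in the model it is s. The variance ratio S²/s² is 18.4, 8.7 and 5.4.

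**Power.** Noncentral t with noncentrality ln(1.3) / (SD × √(1/n1 + 1/n2)), where ln(1.3) = 0.262. The root is 0.365 for 15 v 15 and 0.413 for 8 v 22. Degrees of freedom are 28 pooled, and 30 − 6 = 24 with five cohort means plus the characteristic.

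| s | 15 v 15 pooled | 15 v 15 with dose | 8 v 22 pooled | 8 v 22 with dose |
|---|---|---|---|---|
| 0.2 | 13% | 93% | 11% | 86% |
| 0.3 | 12% | 63% | 11% | 53% |
| 0.4 | 12% | 41% | 10% | 33% |

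Example, 15 v 15, s = 0.3: noncentrality is 0.262 / (0.887 × 0.365) = 0.81 pooled and 0.262 / (0.3 × 0.365) = 2.40 with dose. The columns with dose assume a characteristic roughly balanced over cohorts.

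**Bias and type I error.** Simulation, 6,000 runs per scenario, 8 v 22, CV 30%, no true effect:

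- Random spread over cohorts: the pooled test rejects in 5.0%, although the groups' geometric mean doses differ by more than 1.5-fold in about 26% of trials.
- Moderately late recruitment (weights 1:1:2:2:3 over cohorts 1 to 5): 17%.
- All 8 in cohorts 4 and 5 (an extreme case): 100%. Mean ln dose is 5.120 in the group and 3.949 in the other 22, so the spurious ratio is exp(5.120 − 3.949) = 3.2.
- With cohort in the model, rejection is 4.6% to 5.1% in these three scenarios.

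Adjustment does not make imbalance harmless. For a true 1.5-fold effect, the adjusted model's power is 85% with random spread, 83% with moderately late recruitment and 53% in the extreme case.

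**Where the loss does not arise.** Under linear PK, CL does not depend on dose, and a pooled test has 69% to over 99% power for a 1.5-fold effect (CV 20-40%, both splits). The same reasoning covers t1/2 and Vz. For uncorrected total albumin the documents give no baseline level. As an illustration, assume 35-45 g/L endogenous albumin and a distribution volume of 35-60 mL/kg. The ratio of Cmax at 200 to that at 20 mg/kg is then at most (35 + 200/35) / (35 + 20/35) = 40.71 / 35.57 = 1.14 and at least (45 + 200/60) / (45 + 20/60) = 48.33 / 45.33 = 1.07. The between-dose SD of ln Cmax is 0.024 to 0.050. With an assumed within-dose SD of 0.06 to 0.15, leaving dose out inflates the variance by 1 + (0.024/0.15)² = 1.03 to 1 + (0.050/0.06)² = 1.7.

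**The case against.** The strongest reply is that Section 11.1 is a generic paragraph that never says dose levels will be combined, while Sections 1.1 and 11.4.1 organise the PK summaries by dose level. That is correct: pooling is the natural reading of an unstratified univariate test, not stated text. But the by-dose summaries are descriptive and do not replace the committed tests. The other reading, testing within a cohort, gives at best 3 v 3, with 17-48% power even for a 1.5-fold effect (CV 20-40%).

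A reader might infer that the tests have almost no power for any endpoint. The documents do not support that. Listed parameters such as CL do not depend on dose under linear PK. Section 1.1 presents baseline-corrected parameters in addition to uncorrected ones, for which the loss is small. The analyte is itself unclear: the notes to Table 1 describe the PK sample as serum albumin, Section 7.2 as OsrHSA by immunoassay.

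A reader might also infer that confounding is certain. It is not. It needs uneven spread over cohorts, which the plan does not prevent but does not create either.

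Finally, the consequence is limited. The primary safety endpoints are not tested, the trial is not sized for power, no escalation decision uses these tests, and individual data are plotted by dose. All of that stands. It limits the importance of the point, but gives no reason to commit to the weaker method.

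**Conclusion.** The point holds for dose-dependent endpoints: baseline-corrected or OsrHSA-specific Cmax and AUC, and probably change in albumin or colloid osmotic pressure. For these, a pooled test has about 10-13% power for a 1.3-fold difference where a model with dose has 33-93%, depending on the split and the within-dose SD. Bias is a conditional risk that the overall ethnic minimum does not remove.

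The figures rest on dose-proportional exposure, the assumed SD range (the same at every dose), alpha 0.05 and the assumed group sizes. If subtracting endogenous albumin adds noise at the low doses, the adjusted power would be lower than shown.

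It would go too far to conclude that a real sex or ethnic difference must be missed, or that the primary safety evaluation is affected. This is a correctable weakness in a supporting analysis of secondary and exploratory endpoints.

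**What to change.** In Section 11.1, replace the univariate tests of characteristics with one committed analysis:

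- Name the characteristics. Healthy volunteers have no disease characteristics in the usual sense.
- Among OsrHSA recipients, fit a linear model with dose cohort (or ln dose) plus the characteristic. Add the baseline value for change endpoints.
- Use the log scale only where values are positive. Baseline-corrected values at low doses may be zero or negative.
- Do not rely on dose-normalised parameters, because Section 11.4.1 sets out to test dose proportionality.
- State how placebo subjects are handled. Section 7.2 samples all subjects, and Section 11.3.1 does not exclude placebo from the PK population.
- Report estimates with confidence intervals, label them exploratory, and state that Section 11.4.2 governs safety endpoints.

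The cost is SAP wording, a little more analysis work and up to 4 degrees of freedom (one if ln dose is used). No new data are needed.
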